## 1.0 PROTOCOL SUMMARY AND/OR SCHEMA

This is a single-center, single-arm phase II study to evaluate the efficacy and safety of the anti-IL-5R $\alpha$  chimeric monoclonal antibody benralizumab for the treatment of eosinophil-related cutaneous adverse events (ercAEs) resulting from immunotherapies or targeted therapies. Forty eight (48) patients will be enrolled and the estimated time to completion is 2 years. The primary endpoint for the study is the percent reduction in CTCAE grade 2/3 eosinophil-related cutaneous adverse events to grade  $\leq 1$ . Eosinophil-related cutaneous adverse events are defined as maculopapular rash, pruritus/urticaria, bullous pemphigoid, or DRESS syndrome that are associated with blood eosinophil counts of at least .3 K/mcl. Secondary endpoints are safety and tolerability of benralizumab, calculated rash body surface area (BSA), relative dose intensity (RDI) of anticancer therapy, measurement of patient-reported quality of life, the ability to continue anticancer agents, effects on corticosteroid naïve and dependent/refractory ercAEs, the need for additional supportive care interventions (i.e. corticosteroids, antihistamines), and reduction in blood and skin eosinophils. An exploratory endpoint is analyzing eosinophils and Th2 immune pathway blood biomarkers ( IFN- $\gamma$ , IL-1 $\beta$ , IL-2, IL-4, IL-5, IL-6, IL-8, IL-10, IL-12p70, IL-13, TNF- $\alpha$ , tryptase) that correlate with benralizumab efficacy. Patients with a diagnosis of solid or hematologic cancers undergoing treatment with checkpoint inhibitors (CPIs) or targeted therapies with a grade 2/3 cutaneous adverse associated with blood eosinophil counts of at least .3 K/mcl will be treated with benralizumab 30mg once every 4 weeks for the first 3 doses (Week 0/Day 1, Week 4/Day 28, and Week 8/Day 56), followed by once every 8 weeks for 3 additional doses (Week 16/Day 112, Week 24/Day 168, and Week 32/Day 224). CTCAE v5.0 ercAE assessments will be done at baseline and then at Week 2/Day14, Week 4/Day 28, and Week 8/Day 56, Week 16/Day 112, Week 24/Day 168, Week 32/Day 224 and 4 weeks post-last dose. Patients may remain on study until ercAE progression or unacceptable toxicity from benralizumab for up to 32 weeks.

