### 4.2 Intervention

All eligible patients will receive a benralizumab dose of 30 mg SC administered by a healthcare provider once every 4 weeks for the first 3 doses, followed by once every 8 weeks for 3 additional doses. This is the approved dose and schedule for eosinophilic asthma. Eosinophil-related cutaneous AE assessments will be conducted at baseline, Week 0/Day 1 (+/-3), Week 2/Day 14 (+/-3), Week 4/Day 28 (+/-3), and Week 8/Day 56 (+/-3) using CTCAE v5.0. Patients may remain on study until progression of ercAE or unacceptable toxicity from benralizumab. Patients will continue receiving the investigational agent for up to 32 weeks (6 doses).

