**Missed doses will not be made up.**

## 11.0 EVALUATION DURING TREATMENT/INTERVENTION

Study Procedures	Screening Visit (-7 days to Day 1) 	Week 0/ Day 1	Week 2/ Day 14 (+/- 3 days)	Week 4/ Day 28 (+/- 3 days)	Week 8/ Day 56 (+/- 3 days)	Week 16/ Day 112 (+/- 7 days) 	Week 24/ Day 168 (+/- 7 days) 	Week 32/ Day 224 (+/- 7 days) 	4 Weeks post-last dose (+/- 7 days)
Informed Consent	X 								
Demographics	X								
Medical history	X								
Concomitant medication review	X	X	X	X	X	X	X	X	X
Serum pregnancy test, per SOC and if applicable	X 								
Skin biopsy 	X			X					
CBC with differential	X	X	X	X	X	X	X	X	X
Comprehensive Metabolic Panel	X								
Physical exam and vital signs (HR, BP, weight, and temperature)	X								
Skin Exam (prior to Benralizumab administration)		X		X	X				
ECOG Performance Status (Appendix C)	X								
Total body photography	X	X		X	X				
Eosinophil-related Adverse Event Grading (CTCAE v5.0) (Appendix A)	X	X	X	X	X	X	X	X	X
Research blood collection for biomarker analysis (IL-5 & MSD Panel)		X		X	X				

Adverse event evaluation	X	X	X	X	X	X	X	X	X
Patient self-assessment (PRO-CTCAE (Appendix D) & Skindex 16 (Appendix B)	X	X	X	X	X	X	X	X	X
RegiSCAR Scoring System for Diagnosing DRESS Syndrome		X							
Benralizumab 30mg SC administration		X		X	X	X	X	X	

SOC, standard of care.

1. Informed consent within 45 days prior to treatment.
2. Serum pregnancy test for WOCBP within 14 days prior to treatment.
3. The baseline skin biopsy will be obtained within 30 days of treatment start, if applicable per standard of care. The biopsy at day 28 will be RNB if the patient's symptoms are improving.
4. Assessments will continue as long as the patient continues receiving benralizumab (up to 32 weeks). If a patient discontinues benralizumab, they will move to the 4 weeks post-last dose follow-up visit.
5. Screening and Week 0/Day 1 visits can be combined as long as comprehensive metabolic panel, CBC w/ differential, and pregnancy test (if applicable) are resulted to confirm eligibility prior to first benralizumab injection.

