### 13.2 Criteria for Study Endpoint Evaluability

Patients who are removed from the study prior to starting Benralizumab will be considered inevaluable and replaced. Patients who receive at least one dose of Benralizumab will be included in the evaluation of the primary objective if they have a post-therapy documented clinical response. Patients who progress and are placed on agents instead of or in addition to the culprit agents will be removed from the study. Patients who receive steroids at doses greater than prednisone 20mg a day or equivalent or other immunosuppressive agents to manage additional irAEs will be considered a failure for the primary endpoint.

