**Secondary endpoints:**

**AE-related quality of life:** Quality of life will be assessed for all patients at Week 0/ Day 1, Week 2/Day 14, Week 4/Day 28 and Week 8/Day 56, Week 16/Day 112, Week 24/Day 168, Week 32/Day 224 and 4 weeks post-last dose using PRO-CTCAE and Skindex 16 (Appendix D). Prior to conducting analyses, we will evaluate questionnaire compliance. The amount of missing data across the PRO instruments will be summarized. A questionnaire will be considered complete if enough questions were completed to be a valid score. Since these instruments are broken into sections, completion of any section for a given adverse event will be considered complete information for that adverse event. Baseline characteristics of study participants with completed and incomplete QOL data will be compared in a descriptive manner. Mouth/throat sores, dry skin and itchy skin are reported on a 5-point scale, while rash, hives and sensitivity of the skin to sunlight are reported on a 2-point scale. These symptoms will be summarized using descriptive statistics. The proportion of patients with different levels of these symptoms will be assessed at each study time point along with exact binomial confidence intervals. A summary score for the Skindex-16 will be calculated for each participant at each time point. The total Skindex-16 score will be summarized for each study time point along with 95% confidence intervals.

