**Safety and tolerability of benralizumab:** This endpoint will be measured in terms of CTCAE v5.0 ercAE. The proportion of patients with different grade categories (0, 1, 2 etc) will be assessed at each study time point along with exact binomial confidence intervals. Patients progressing to grade 4 ercAE will be removed from the study (Section 12.0). The proportion of such patients at each time point will be reported. The proportion of patients having a reduction and the proportion having an increase in ercAE grade category will be reported.

**Need for supportive medication:** The proportion of patients requiring supportive medications such as corticosteroids, antihistamines and immunosuppressants will be reported at each time point along with exact binomial confidence intervals.

**Effect of benralizumab on subsequent planned cycles of checkpoint inhibitors (CPIs) or targeted therapies:** We will measure changes in blood eosinophil levels between baseline and cycles of various planned treatments for these patients, and report the mean, standard deviation, range and number of patients scheduled to receive different therapies.

**Effect of benralizumab on corticosteroid naïve and corticosteroid dependent/refractory ercAEs:** Corticosteroid naïve patients are those not receiving corticosteroids for 14 days since Week 0/Day 1 of benralizumab treatment. Corticosteroid dependent/refractory ercAEs are patients that are on prednisone 10mg a day or greater at the initiation of study. We will report the number of corticosteroid naïve and dependent/refractory ercAE patients, measure change in blood eosinophil levels between Week 0/Day 1 and Week 8/Day 56, report descriptive statistics such as mean, standard deviation and range in these groups of patients.

**Effect on eosinophil counts:** Changes in eosinophil counts will be calculated and reported as percent reduction +/- standard deviation. In addition to comparing baseline and end-of-study percent change in eosinophils, we will also compare percent changes across baseline ercAE categories and end-of-study ercAE categories. We will use regression models to examine the association between longitudinal measurements of percent change in eosinophils at Week 0/Day 1, Week 2/Day 14, Week 4/Day 28, and Week 8/Day 56, Week 16/Day 112, Week 24/Day 168, Week 32/Day 224 and 4 weeks post-last dose and longitudinal measurements of ercAE categories.

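### Week 16, 24 and 32 ercAE grades and PROs are collected only while patients stay on benralizumab, and the plan does not say how dosed patients who have stopped are counted

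*Combined protocol and SAP*

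**What the plan says.** Footnote 4 to the Section 11.0 schedule is attached to the Week 16, 24 and 32 columns only: "Assessments will continue as long as the patient continues receiving benralizumab (up to 32 weeks". It continues: "If a patient discontinues benralizumab, they will move to the 4 weeks post-last dose follow-up visit".

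Several passages tie leaving to the course of the skin event or to toxicity:

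- Section 1.0: "Patients may remain on study until ercAE progression or unacceptable toxicity from benralizumab for up to 32 weeks". Section 4.2 repeats the rule: "Patients may remain on study until progression of ercAE or unacceptable toxicity from benralizumab".
- Section 13.2: "Patients who progress and are placed on agents instead of or in addition to the culprit agents will be removed from the study". It does not say whether ercAE or cancer progression is meant.
- Section 14.1, Safety and tolerability: "Patients progressing to grade 4 ercAE will be removed from the study (Section 12.0".

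Section 14.1 analyses the late visits as follows. For ercAE grade: "The proportion of patients with different grade categories (0, 1, 2 etc) will be assessed at each study time point", with exact binomial intervals. For the PRO-CTCAE items: "The proportion of patients with different levels of these symptoms will be assessed at each study time point along with exact binomial confidence intervals". The total Skindex-16 score is summarised by visit with 95% intervals.

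The opening of Section 14.1 defines evaluable as having had at least one dose. It bases secondary analyses on evaluable patients, giving both 48 and 28 as their number (a separate conflict to reconcile). Removed patients are summarised separately, using data up to removal. The only imputation of a missed visit is for Skindex-16 at Week 4.

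**The concern.** From Week 16 the plan has scheduled data only for patients still being dosed, and some reasons for no longer being dosed are the outcome itself. A patient whose rash progresses in Week 12 has no Week 16, 24 or 32 grade. If the tables use whoever was assessed, that patient disappears from the denominator. The share at grade ≤1 can then rise from visit to visit with no individual improving, and the exact interval describes a selected group as though it were the treated cohort.

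These visits are the trial's only information on what happens between Week 8 and Week 32, and there is no control arm against which such selection would show. The same depleted visits feed the PRO tables, the supportive-medication proportions and the longitudinal regression of eosinophil change on ercAE category.

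**Working it through.** **Plan's own figure.** The plan states none for Weeks 16 to 32. Its one quantitative claim is more than 80% power at Week 4. For 17 or more responders of 28, 40% against 70%, the exact binomial gives 89.7% power and a one-sided type I error of 0.0215, consistent with the claim. It has no bearing on the late visits.

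**Can the follow-up visit fill the gaps?** Doses fall at Weeks 0, 4, 8, 16, 24 and 32. Four weeks after each is Week 4, 8, 12, 20, 28 or 36. None is Week 16, 24 or 32, and with windows of ±7 days on both sides the nearest pairs (12 and 16, 20 and 24, 28 and 32) do not overlap. The visit does collect grade and PROs from leavers, but at other times.

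**Formula.** Let r be the true share of all dosed patients at grade ≤1 (controlled), c the share of controlled patients still on drug, and u the share of uncontrolled patients still on drug. Nobody's grade changes. The on-drug proportion is

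P = r·c / [r·c + (1 − r)·u].

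The documents give none of r, c or u for these visits, so every value below is an assumption.

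- r = 0.50, c = 0.85, u = 0.30: 0.425 / (0.425 + 0.150) = 0.739. Gap 74 − 50 = 24 points.
- r = 0.50, c = 0.85, u = 0.50: 0.425 / (0.425 + 0.250) = 0.630. Gap 63 − 50 = 13 points.
- r = 0.40, c = 0.85, u = 0.30: 0.340 / (0.340 + 0.180) = 0.654. Gap 65 − 40 = 25 points.
- Exit unrelated to response, r = 0.50, c = u = 0.85: 0.425 / 0.850 = 0.500. No gap.
- Controlled patients leaving more often, r = 0.50, c = 0.50, u = 0.85: 0.250 / 0.675 = 0.370. The figure is too low.

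Milder and stronger retention patterns, with the number left of 48:

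| True r | c | u | On-drug P | On drug, of 48 |
|---|---|---|---|---|
| 70% | 95% | 75% | 74.7% | 42.7 |
| 70% | 90% | 50% | 80.8% | 37.4 |
| 70% | 90% | 25% | 89.4% | 33.8 |
| 40% | 95% | 75% | 45.8% | 39.8 |
| 40% | 90% | 50% | 54.5% | 31.7 |
| 40% | 90% | 25% | 70.6% | 24.5 |

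**What an all-dosed analysis would show.** Take r = 0.50, c = 0.85, u = 0.30. Of all dosed patients, 42.5% are controlled and on drug, 0.50 × 0.15 = 7.5% are controlled leavers, and 0.50 × 0.70 = 35% are uncontrolled leavers. If every uncontrolled leaver left for ercAE progression or rescue (counted as not grade ≤1) and every controlled leaver for another reason (bounded), the range is 42.5% to 42.5 + 7.5 = 50%, which includes the true 50%. If only half of the uncontrolled leavers left for those reasons, it widens to 42.5 + 7.5 + 17.5 = 67.5%. The width shows how much the late figure depends on unknown outcomes.

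**The case against.** The strongest reply is that the plan never says the late denominator is patients on drug. Section 14.1 bases secondary analyses on evaluable patients, meaning anyone dosed. That is right, and a reader who infers that the written plan prescribes an on-drug denominator goes too far. But naming the analysis set does not say what to enter for a member with no Week 16 grade, and an observed-case table is the likely default. The gap stands.

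A reader might also infer that non-responders leave, so that late denominators hold mainly responders. The documents do not support this. Section 13.1 separates a nonresponding event from a progressive one, and no rule requires a stable non-responder to stop. Section 12.0 allows exit for non-compliance, investigator judgement or withdrawn consent, which can remove responders. If Section 13.2 means cancer progression, that exit is not directly tied to the skin outcome; Sections 1.0 and 4.2 name ercAE progression and carry the argument alone. Upward distortion is therefore an expectation under a stated condition, not a certainty.

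A third inference is that 74% should be set against 42.5%, and 65% against 0.40 × 0.85 = 34%. Those comparators count controlled patients who left as failures. They are floors; the assumed true rates are 50% and 40%.

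Finally, the plan already discloses a good deal: reasons for removal, ercAE categories before removal, grade 4 removals by visit, the amount of missing PRO data, and a descriptive comparison of patients with complete and incomplete QOL data. This helps a careful reader but does not correct the late-visit proportions. It is also fair that these are descriptive secondary results and that no durability endpoint is named.

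**Conclusion.** The concern holds in a limited form. Late assessments stop with treatment, stopping is partly tied to ercAE progression, grade 4 ercAE or toxicity, and no rule covers dosed patients without a late assessment. Observed-case results at Weeks 16, 24 and 32 can be expected to look better than the dosed cohort if patients who progress or stop are less often at grade ≤1.

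Under the retention assumed in the main illustration the excess is 13 to 25 points; across the wider table it runs from about 5 points (74.7 against 70) to about 31 (70.6 against 40). All of it rests on assumed retention and unchanged grades, and it is zero when exit is unrelated to response.

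A reader should not infer that the trial's main conclusion is at risk: the primary endpoint is read at Week 4, and footnote 4 does not touch it. This is an inexpensive improvement to secondary reporting.

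**What to change.** Leave treatment, visits and exit rules as they are, and add to Section 14.1:

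1. **ercAE response at Weeks 16, 24 and 32.** Report the proportion at grade ≤1 with all dosed patients as denominator. Count patients who left for ercAE progression or rescue as not grade ≤1. Bound all other leavers by best and worst case, including those who left for toxicity, whose skin may be clear.
2. **Grade-category table.** Show leavers in a separate off-treatment row, split by reason, rather than assigning them a grade.
3. **ercAE and PRO tables.** Print the number on drug and the number assessed at each visit. Label observed-case proportions, their intervals and the Skindex-16 means as on-treatment only.

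The cost is analysis-plan wording and table shells. No new data are needed, since reasons for removal are already to be summarised, and Section 13.2 already counts certain steroid or immunosuppressant use as failure for the primary endpoint. The late figures will look less favourable, and the bounds will be wide if many patients leave for other reasons.

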## 12.0 CRITERIA FOR REMOVAL FROM STUDY

- Patients may be removed from the study for protocol non-compliance with visits.
- If at any time the patient develops unacceptable toxicity he/she will be removed from study.
- Participants can be removed from the study at any time if the investigator considers that it is in their best interest to do so.
- Patients may withdraw consent from the study at any time.

## 13.0 CRITERIA FOR OUTCOME ASSESSMENT AND ENDPOINT EVALUABILITY

Please refer to Section 11.0 regarding the timing of ercAE assessments. Documentation (photographic) must be provided for patients removed from study for ercAE progression. Response and ercAE severity will be evaluated in this study using the Common Terminology Criteria for Adverse Events version 5.0. Changes in severity grade by specific skin/subcutaneous tissue AE term will be used.

### 13.1 Criteria for Therapeutic Response/Outcome Assessment

Evaluation of ercAE by CTCAE v5.0

Response (R): Grade 2 or 3 event reduction to grade 0 or 1.

Nonresponding AE (nrAE): Grade 2 or 3 event that does not reduce to grade 0 or 1.

Progressive AE (pAE): Grade 2 event that increases by  $\geq 1$  grade in severity.

### 13.2 Criteria for Study Endpoint Evaluability

Patients who are removed from the study prior to starting Benralizumab will be considered inevaluable and replaced. Patients who receive at least one dose of Benralizumab will be included in the evaluation of the primary objective if they have a post-therapy documented clinical response. Patients who progress and are placed on agents instead of or in addition to the culprit agents will be removed from the study. Patients who receive steroids at doses greater than prednisone 20mg a day or equivalent or other immunosuppressive agents to manage additional irAEs will be considered a failure for the primary endpoint.

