## 6.0 CRITERIA FOR PARTICIPANT ELIGIBILITY

### 6.1 Participant Inclusion Criteria

- Patients must have pathologically or cytologically confirmed solid or hematologic cancers.  
OR
- Patient is receiving alpelisib for PIK3CA-Related Overgrowth Spectrum disorder.
- Female and male aged 18 to 85 years, inclusively, at the time of Week 0/Day 1 of treatment.
- Patients must have a therapy-related CTCAE grade 2/3 (See Appendix A) cutaneous adverse event defined as any cutaneous reaction listed below and blood eosinophil counts of at least .3 K/mcl.
  - Rash maculo-papular
  - Bullous dermatitis
  - Pruritus
  - Urticaria
  - Eczema
- Patients must plan to continue on culprit drugs (cancer patients).
- Patients planning to receive alpelisib indicated for PIK3CA-Related Overgrowth Spectrum disorder OR patients receiving immunotherapy and/or targeted therapy, including but not limited to the following agents, will be eligible for inclusion:
  - Immunotherapies: ipilimumab, nivolumab, pembrolizumab, avelumab, durvalumab, atezolizumab, tremelimumab.
  - Targeted therapies: trastuzumab, pertuzumab, alpelisib, osimertinib, everolimus, temsirolimus, sorafenib, regorafenib.
- Patients using topicals/orals for indication of skin rash/pruritus for at least 7 days should continue using these drugs for the study duration.
- Adequate bone marrow, liver and renal function:
  - Total bilirubin  $\leq$  1.5 x the upper limit of normal (ULN)
  - Alanine aminotransferase (ALT) and aspartate amino-transferase (AST)  $\leq$  2.5 x ULN ( $\leq$  5 x ULN for subjects with liver involvement of their cancer)
  - Alkaline phosphatase  $\leq$  2.5 x ULN ( $\leq$  5 x ULN for subjects with liver involvement of their cancer)
  - Serum creatinine  $\leq$  1.8 xULN or calculated creatinine clearance  $>45$  ml/min

- Platelet count > 50 K/mcL, hemoglobin (Hb) > 8 g/dL, absolute neutrophil count (ANC) > 1.0 K/mcL. Blood transfusion to meet the inclusion criteria will not be allowed.
- ECOG performance status 0-1 (see Appendix C).
- Subjects must be able to understand and be willing to sign the written informed consent form. A signed informed consent form must be appropriately obtained prior to the conduct of any trial-specific procedure.
- Female patients are authorized to participate if they meet the following criteria:
  - Women of child bearing potential must meet both of the following conditions:

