## 6.2 Participant Exclusion Criteria

- Concurrent use of another investigational drug or device for the ercAE (i.e., outside of study treatment) during, or within 4 weeks of treatment.
- Patients receiving prednisone  $\geq$  20mg a day.
- Known use of anti-IL-5 agents or biologics for the treatment of asthma which are known to decrease blood eosinophil levels.
- Patients cannot use new topicals or medications for indication of pruritus or skin rash
- Known history of anaphylaxis to biologic therapy
- A helminthic parasitic infection diagnosed within 24 weeks prior to the first treatment, that had not been treated with, or has failed to respond to, standard of care therapy.
- Known history of human immunodeficiency virus (HIV) infection or current chronic or active hepatitis B or C infection requiring treatment with antiviral therapy.
- Active infection that would impair the ability of the patient to receive study treatment.
- Women who are pregnant or breast-feeding.

- Any condition which, in the investigator's opinion, makes the subject unsuitable for trial participation.
- Receipt of live attenuated vaccines 30 days prior to the date of randomization
  - Receipt of inactive/killed vaccinations (e.g., inactive influenza) is allowed provided they were not administered within 1 week before/after any investigational product administration.
- Known history of allergy or reaction to the investigational product formulation

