## 14.0 BIOSTATISTICS

This is a single-center single-arm phase II study to evaluate the efficacy and safety of benralizumab for the treatment of eosinophil-related cutaneous adverse events (ercAE) in patients having grade 2/3 ercAE to various treatments (such as checkpoint inhibitors or targeted therapies) with blood eosinophil counts of at least .3 K/mcL.

The primary endpoint of efficacy is defined as the proportion of patients who have a reduction from CTCAE grade 2/3 eosinophil-related cutaneous adverse events to grade  $\leq 1$  following treatment with benralizumab. The study will be declared positive if  $\geq 70\%$  of patients have a reduction of grade 2/3 eosinophil-related cutaneous adverse events to grade  $\leq 1$  (between Week 0/Day 1 and Week 4/Day 28).

Data from medical oncology and other MSK visits will be collected at the last study visit for each patient and immune related adverse events with grade and attribution will be included in the final analysis.

Data analysis will be conducted by externally funded biostatistician (consultant), [name] of Augmentium Pharma Consulting Inc. The Consultant will serve to review, analyze, and assess data, documents and information provided from MSK, which shall be MSK's Confidential Information, and provide subsequent guidance in a format. The Consultant will also provide independent information to support MSK's clinical research activities. Additional projects that are beyond the scope of this WP will require a separate document executed in writing between the Parties. The Services shall be provided by Consultant at the direction and discretion of MSK and all deliverables or other materials produced by the Consultant shall be subject to Section 5 of the Agreement. The consultant will have access to participant PHI including name, demographics (DOB, age, gender, race, ethnicity), medical history (treatment start and end date and treatment information) and questionnaire responses. Details of this contract are available on the PIMS regulatory binder.

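### Section 13.2 does not clearly fail patients whose study rash itself is treated with extra steroids or immunosuppressants, and grade-only scoring then counts them as responders

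*Combined protocol and SAP*

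**What the plan says.** **Response.** Section 13.1 defines it by grade only: "Response (R): Grade 2 or 3 event reduction to grade 0 or 1". Section 14.0 repeats this for the primary endpoint, with no condition on other rash treatment. On the success rule it says "The study will be declared positive if" at least 70% of patients make that reduction between Day 1 and Day 28.

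**Failure because of other therapy.** Section 13.2 has the only such rule. Patients on steroids above the equivalent of prednisone 20 mg/day, or on other immunosuppressive agents, "to manage additional irAEs will be considered a failure for the primary endpoint".

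**Conduct rules.** Section 6.2 states: "Patients cannot use new topicals or medications for indication of pruritus or skin rash". It also excludes patients on prednisone 20 mg/day or more at entry. Section 6.1 states: "Patients using topicals/orals for indication of skin rash/pruritus for at least 7 days should continue using these drugs for the study duration". Neither section says how a breach is scored, and neither mentions a dose increase.

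**Supportive medication.** Under the secondary endpoints in Section 14.1, steroid-dependent or refractory patients are those "on prednisone 10mg a day or greater at the initiation of study". Supportive drugs are summarised descriptively: "The proportion of patients requiring supportive medications such as corticosteroids, antihistamines and immunosuppressants will be reported at each time point". In the Section 11.0 schedule, "Concomitant medication review" is marked at every visit.

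**The concern.** There is no control arm, so the response rate is the whole of the efficacy evidence. If the rash settles after a steroid increase or an added antihistamine, the grade at Week 4 cannot show which treatment did it. Section 13.1 nevertheless credits the improvement to benralizumab. The failure rule in 13.2 shows that the authors meant some concurrent treatment to disqualify a response, but its wording points at other immune-related events and leaves the study rash uncertain. At stake is how the reported response rate should be read, above all if it lands close to the 70% bar.

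**Working it through.** **1. The plan's own figure.** Inputs from Section 14.1, primary endpoint: n = 28, reference 40%, expected rate 70%, cut-off 17 responders, alpha 5% (side not stated). With P(X ≥ r) = Σ C(28,k) p^k (1−p)^(28−k), summed over k = r to 28:
- P(X ≥ 17) at p = 0.40 is 0.0215.
- P(X ≥ 17) at p = 0.70 is 0.897, which agrees with the stated power of more than 80%.

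For the 70% rule, 0.70 × 28 = 19.6, so 20 responders are needed. P(X ≥ 20) is 0.00076 at 40% and 0.528 at 70%.

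**2. What 13.2 reaches.** The qualifier about additional irAEs can attach to both drug classes (reading A) or only to the immunosuppressants (reading B).

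| Given for the study rash before Week 4 | Reading A | Reading B |
|---|---|---|
| Steroids above prednisone 20 mg/day | not covered | failure |
| Other immunosuppressants | not covered | not covered |
| Prednisone raised to at most 20 mg/day | not covered | not covered |
| Topical steroid or antihistamine, new or escalated | not covered | not covered |

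Wherever 13.2 does not apply, 13.1 decides, and grade 0-1 is a response. A newly started drug in this table breaches 6.2, but no scoring consequence follows.

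**3. Escalation without a breach.** Entry is allowed below 20 mg/day (6.2). The steroid-dependent subgroup enters on 10 mg/day or more (14.1). Failure starts only above 20 mg/day (13.2). A rise from 10 to 20 mg/day for the rash falls between these limits.

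**4. One patient, with no rescue rate assumed.**
- 70% rule: 20/28 = 71.4% passes and 19/28 = 67.9% does not.
- 17/28 cut-off: the exact p-value against 40% is 0.022 one-sided or 0.033 two-sided. At 16/28 (57.1%) it is 0.0499 or 0.081.

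**5. Illustration only.** Let f be the share of true non-responders brought to grade 0-1 by other therapy, with f = 0.10 assumed. Let g be the rescue effect, in the same sense, already inside the 40% reference. The rescue-free rate is p0 = (0.40 − g)/(1 − g), and the observed rate is p0 + (1 − p0) × 0.10.

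| g | p0 | Observed rate | P(X ≥ 17) | P(X ≥ 20) |
|---|---|---|---|---|
| 0 | 0.400 | 0.460 | 0.085 | 0.0058 |
| 0.05 | 0.368 | 0.432 | 0.047 | 0.0023 |
| 0.10 | 0.333 | 0.400 | 0.022 | 0.00076 |

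So for f = 0.10 the false-positive rate lies between 2.2% and 8.5% at 17/28, and between 0.08% and 0.6% under the 70% rule, depending on what the reference contains.

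**6. Near the bar.** At an assumed true rate of 60%, the observed rate is 0.60 + 0.40f. P(X ≥ 20) is 14.8% for f = 0, 20.4% for f = 0.05 and 27.1% for f = 0.10.

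**The case against.** The strongest reply is that the conduct rules already deal with most of this. New rash or itch medication is barred by 6.2, and established drugs are to continue under 6.1. A new topical or antihistamine is therefore a deviation, not routine care that the plan allows and then rewards. Section 15.0 speaks only of gradual steroid reduction on benralizumab, never of an increase. That stands, and it narrows the point to two things: how a deviation is scored, and how an escalation is scored.

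A reader might infer more from three places, and in each the documents stop short.

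- *That rescue is expected because supportive medication is tabulated at each visit.* That proportion also includes the background therapy that 6.1 tells patients to continue. It is not evidence of new or escalated treatment.
- *That rescue would work, because Section 3.0 says steroids and stopping the culprit drug may help most patients.* That sentence joins the two measures. Here cancer patients must plan to stay on the culprit drug, and much of the uncovered treatment is low-dose steroid, topical or antihistamine. The sentence makes an alternative cause plausible but does not show it.
- *That the comparison with 40% is biased.* Section 14.1 describes the 40% as grade improvement under other treatment regimens, from clinical experience. A grade-based rate that tolerates supportive care may be the like-for-like comparison.

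It is also fair to say that any threshold can turn on one patient, so step 4 shows sensitivity, not frequency. Finally, Appendix A is listed by title only in the text available here, so whether the grade definitions take account of treatment cannot be checked.

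None of this answers the scoring gap. As written, an escalated patient at grade 0-1 is a responder, and the descriptive table of supportive drugs is not linked to response.

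**Conclusion.** The gap is real and narrow. Section 13.2 does not clearly cover high-dose steroids given for the study rash. On either reading it does not cover other immunosuppressants for the rash, or escalation of existing therapy up to prednisone 20 mg/day. Grade-only scoring then credits such patients to benralizumab.

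The direction is certain: the observed response rate can only go up. The size is not known, because no rescue rate is given and every figure in steps 5 and 6 rests on assumed fractions. At a true rate of 40% the effect under the 70% rule is small (at most 0.6% false positives with 10% rescued). It matters mainly when the result is close to the bar.

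The 8.5% figure should not be read as the trial's error rate. It needs a reference with no rescue in it, which fits poorly with a rate taken from other treatment regimens, and it applies to the 17/28 cut-off in the power statement rather than to the declared 70% rule. Nor does the evidence call for replacing the grade-based primary endpoint. The plan should be clarified and one sensitivity analysis added.

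**What to change.** 1. Amend 13.2 so that steroids above prednisone 20 mg/day, or other immunosuppressants, are failures for the primary endpoint when given for the study rash as well as for additional irAEs. Section 14.1 says the initial 28 patients were already accrued when the expansion cohort was added. If their outcomes are known, apply this only as a sensitivity analysis, so that the endpoint is not redefined after its results.
2. Otherwise keep the grade-based primary definition.
3. Add one pre-specified sensitivity analysis that scores any new or escalated rash- or itch-directed corticosteroid, antihistamine or immunosuppressant before the Week 4 grading as non-response. Report both rates side by side.

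Care does not change. The cost is one amended sentence, one analysis paragraph, and coding of indication and dose change from the medication review already done at every visit.

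The sensitivity rate may be lower and less comparable with the 40% reference, which is why both rates are needed. With a 70% response rate and a share r of responders reclassified, p = 0.70 × (1 − r). For r = 0, 0.05 and 0.10, the chance of reaching 17/28 is 89.7%, 80.4% and 67.7%, and of reaching 20/28 it is 52.8%, 37.0% and 23.6%. These shares are assumptions.
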